### Study Assessments and Activities

All patients will undergo the scheduled operation per routine. Post operatively, all usual medications for pain control and bowel movements will be ordered according to institutionally approved and reviewed post-operative order sets. All home medications will also be reconciled and restarted as deemed clinically appropriate by the interdisciplinary care team. Oral naloxone 4 mg enterally every 8 hours will be initiated on post-operative day 1 at 0900. Study drug will be discontinued as described in the study protocol, after 48 hours, or upon discharge whichever is sooner.

### **III. Safety Monitoring Plan**

Definition of adverse events, serious adverse events

Adverse event: Any reported or observed event that is not part of the usual post-operative clinical course.

Serious adverse event: Any event that requires discontinuation of the study drug

Any serious adverse events will be reported immediately to the IRB. All identified adverse events will be reported in the final analysis of this study. Upon completion of data collection, all adverse events will be evaluated by study personnel and adjudicated for their relation to study drug.

What procedures will be used to monitor subject safety

Patients will be monitored for adverse effects via routine vital signs, pain, and neurological assessment every 1 – 4 hours and evaluation for emesis, bowel movements, and diaphoresis. These evaluations do not represent an additional burden to the patient since they are a part of routine post-operative care.

Protected health information and data security

All protected health information associated with the historical cohort will be stored in a password protected Microsoft Excel file on the SSOM Research secured drive. De-identified patient information will be entered into a RedCap database for data collection. All signed consent forms will be collected and securely kept in the patients' medical record through EPIC.

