### **I. Study Aims**

The current study will assess the safety and efficacy of an enteral formulation of the opioid antagonist naloxone in prevention of post-operative ileus and opioid induced constipation.

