### **I. Study Design**

This is a prospective, historically controlled observational trial of enteral naloxone use in patients admitted for spinal fusion surgery and receiving opioids for pain management.

Primary outcome: Time to first bowel movement (hours)

Secondary outcomes:

- Hospital length of stay
- Incidence of post-operative ileus. Post-operative ileus will be diagnosed through a combination of clinical exam and radiographic (X-ray) findings
- incidence of post-operative constipation (defined as 3 days without a bowel movement)
- average numerical pain scale (Adult Nonverbal Pain scale or Visual Analog Scale) on post-operative days 0, 1, 2, and 3
- average daily opioid requirement on post-operative days 0, 1, 2 and 3 (morphine equivalents)
- number of naloxone doses administered
- average number of daily bowel movements,
- number of medication escalations required (defined as use of an as needed laxative medication or addition of a new order for a laxative medication)
- Incidence of adverse effects
- Incidence of study drug discontinuation

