### Toxicities and guidelines for adjustments

Potential adverse effects associated with the use of enteral naloxone have been associated with abrupt reversal of opioid activity with the most uncomfortable or dangerous of these being antagonism of central opioid activity and loss of pain control. Additional adverse effects include nausea, vomiting, diarrhea, hypertension, tachycardia, diaphoresis, and mental status changes. Patients will be monitored for adverse effects via routine vital signs, pain score, and neurological assessment every 1 – 4 hours and evaluation for emesis, bowel movements, and diaphoresis. Study drug will be discontinued in patients who meet any three of six criteria within 1 hour of study drug administration:

1. Heart rate increases > 20 beats per minute for > 5 minutes
2. Respiratory rate increases to > 20 breaths per minute
3. Diaphoresis
4. Pain score increases by > 50%
5. Emesis
6. Diarrhea (defined as > 1 large, liquid bowel movement within 1 hour)

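### The adverse event definition lets naloxone's own named toxicities be set aside as usual post-operative events before relation to drug is judged

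*Combined protocol and SAP*

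**What the plan says.** Safety is part of the stated purpose. Under Study Aims, the study will "assess the safety and efficacy of an enteral formulation of the opioid antagonist naloxone". Study Design lists "Incidence of adverse effects" as a secondary outcome without defining it further. The Analysis Plan compares the two groups on it with a generalized linear mixed effects model, as for every secondary outcome other than length of stay.

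The section on toxicities and guidelines for adjustments names what naloxone may do. The most serious effect is "antagonism of central opioid activity and loss of pain control". Further effects are "nausea, vomiting, diarrhea, hypertension, tachycardia, diaphoresis, and mental status changes". The drug is stopped in patients who "meet any three of six criteria within 1 hour of study drug administration".

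The Safety Monitoring Plan gives the only definition of an adverse event: "Any reported or observed event that is not part of the usual post-operative clinical course". A serious adverse event is "Any event that requires discontinuation of the study drug". Identified adverse events go into the final analysis. After data collection ends, study personnel judge whether those events are related to the drug. Study Intervention states that the study is not blinded.

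**The concern.** The filter works on how ordinary an event looks after surgery, and a drug that makes ordinary events more frequent does its harm in exactly that category. A patient who vomits or becomes tachycardic after a dose may look no different from many post-operative patients. Each event, judged singly, can be called usual even if the cohort as a whole has an excess.

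The order of the steps matters. Deciding that an event is usual is in effect a judgement of cause, made without written criteria and with knowledge of treatment. The planned adjudication covers only events already classed as adverse, so it cannot recover those set aside. The likely error is a naloxone event rate that is too low, on an outcome that answers half of the study aim.

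**Working it through.** **The plan's own figure.** The only design figure is 80.1% power for the primary comparison. With 150 × 0.55 + 150 × 0.70 = 187.5 events and a hazard ratio of 1.508, Schoenfeld's formula gives Φ(√187.5/2 × ln 1.508 − 1.96) = Φ(0.85) = 80.3%. It reproduces, and this point does not touch it.

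**What else would catch each named effect.** The table sets the named effects beside the six discontinuation criteria and the secondary outcomes in Study Design.

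| Named effect | Among the six criteria | Other secondary outcome |
|---|---|---|
| Loss of pain control | Yes (pain score rise) | Average pain score, opioid requirement |
| Nausea | No | None |
| Vomiting | Yes (emesis) | None |
| Diarrhea | Yes | Daily bowel movements, in part |
| Hypertension | No | None |
| Tachycardia | Yes (heart rate rise) | None |
| Diaphoresis | Yes | None |
| Mental status changes | No | None |

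Five of the eight effects match a discontinuation criterion. The remaining criterion, respiratory rate, is not on the list of effects. Vomiting, tachycardia and diaphoresis reach the results by that route only when three criteria coincide within an hour of a dose. One or two such signs, and any nausea, hypertension or mental status change, depend on being classed as an adverse event. Daily average pain can also dilute a brief rise after a dose.

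**Illustration of size.** The documents give no event rates, so all rates here are assumptions. Take one sign that occurs in p₁ = 20% of controls and p₂ = 30% of naloxone patients, with n = 150 per group, two-sided alpha 0.05 and matching ignored. Suppose that a fraction c of occurrences is counted, the same in both groups. The counted rates are then c·p₁ and c·p₂. With these as the two rates and p̄ as their mean,

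power = Φ{[difference − 1.96·√(2p̄(1−p̄)/n)] / √[(p₁(1−p₁)+p₂(1−p₂))/n]}.

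- All counted, 20% v 30%: (0.100 − 1.96 × 0.0500)/0.0497 = 0.04, power 52%.
- Half set aside, 10% v 15%: (0.050 − 1.96 × 0.0382)/0.0381 = −0.65, power 26%.
- 90% set aside, 2% v 3%: (0.010 − 1.96 × 0.0180)/0.0180 = −1.41, power 8%.

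The visible difference falls from 10 points to 5 and then to 1. Across control rates of 10% to 40% and true differences of 10 to 15 points, power is 41–93% with full counting, 18–63% with half counted and 6–17% with a tenth counted.

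**The case against.** The strongest reply is that the outcome is worded as adverse effects, the term used in the toxicities section, while the filter belongs to the separate term adverse event. On that reading the outcome counts the named effects unfiltered. The documents never link the two terms, so this reading is open. It does not remove the problem. The filtered definition is the only one given, and it governs what is reported and adjudicated.

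A second reply is that backstops exist. This stands, and it makes the loss partial, as the table shows.

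Four stronger readings are tempting, and the documents do not support them.

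- A reader might infer that nearly all the named toxicities are usual after fusion. No section says which are. Diarrhea fits poorly in a protocol concerned with ileus and constipation.
- A reader might infer that emesis or a pain rise would go unrecorded. The protocol requires these to be assessed, and the discontinuation rule cannot be applied otherwise. What is at risk is their classification.
- A reader might infer that the study could report no events in 150 patients. That requires every occurrence to be set aside and no patient to meet the discontinuation rule, so it is one extreme case and not an estimate.
- A reader might see a contradiction in three individually usual signs making a serious adverse event. The serious definition refers to any event, and three signs together soon after a dose can fall outside the usual course although each alone does not.

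It is also fair to say that the documents do not state who classifies an event, or when.

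**Conclusion.** The concern holds in limited form. The definition, applied as written, allows some of the toxicities the study is meant to assess to be set aside before relation to drug is judged, and no later step brings them back. The exposure is greatest for nausea, hypertension and mental status changes, and for isolated vomiting, tachycardia or diaphoresis.

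Two assumptions carry this: that some of these effects are regarded as usual after surgery under opioids, which is a clinical judgement, and that staff apply the filter as worded. How much would be lost is unknown, and the power figures show only how sensitive the comparison is under assumed rates and equal filtering in both cohorts. The primary analysis and its stated power are unaffected. The change should be made because safety is a stated aim and the definition can bias the answer in one direction.

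**What to change.** In the Safety Monitoring Plan, state that the usual-course filter does not apply to the effects named in the toxicities section. In Study Design, define the adverse effects outcome as any charted occurrence of each named effect, reported effect by effect, within a fixed post-operative window. Start the window at the scheduled first-dose time, which Study Assessments and Activities gives as 0900 on post-operative day 1. Historical controls have no first dose, so use the same post-operative clock window for them. The comparison in the Analysis Plan is then like for like. Judge relation to drug only at the adjudication already planned.

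The cost is modest. The Safety Monitoring Plan describes the assessments as part of routine care, so the change needs wording, more events to list and extra chart abstraction for the 150 controls. The downside is that reported rates will be higher and will include background post-operative events, so the naloxone rate must be read against the controls. No change to dosing or stopping rules is proposed.

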### Study Intervention

Active study agents: Naloxone

Blinding/labeling/preparation of agents: No blinding is required in this study. The study drug will be prepared, unit dose labelled, and patient labelled according to institutional protocols.

Storage: Secured at room temperature in the central pharmacy then dispensed as a patient specific supply and stored at room temperature the automated dispensing cabinet. No more than a 24 hour supply will be dispensed at any given time.

Administration: 4 mg of a 1 mg/ml oral solution administered enterally (oral, nasogastric, orogastric, gastrostomy, or jejunostomy) every 8 hours for 48 hours

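### Seriousness is defined only by the need to stop study drug, so a new grave event arising after study drug has ended cannot be an SAE and has no stated immediate report to the IRB

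*Combined protocol and SAP*

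**What the plan says.** The Safety Monitoring Plan (section III) defines two classes of event. An adverse event is anything reported or observed outside the normal course after surgery. The serious class has one criterion: "Serious adverse event: Any event that requires discontinuation of the study drug".

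The two classes are reported differently. For the serious class, "Any serious adverse events will be reported immediately to the IRB". For adverse events in general, "All identified adverse events will be reported in the final analysis of this study". Causality comes late: "Upon completion of data collection, all adverse events will be evaluated by study personnel and adjudicated for their relation to study drug".

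The dosing period is short and has fixed ends. Under Study Assessments and Activities, "Oral naloxone 4 mg enterally every 8 hours will be initiated on post-operative day 1 at 0900", and "Study drug will be discontinued as described in the study protocol, after 48 hours, or upon discharge whichever is sooner". Study Intervention gives the same schedule as "every 8 hours for 48 hours". The stopping rule is under Toxicities and guidelines for adjustments: "Study drug will be discontinued in patients who meet any three of six criteria within 1 hour of study drug administration".

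**The concern.** A seriousness definition should pick out events by how grave they are. This one picks them out by their effect on dosing, so it can operate only while there is dosing to stop. Once study drug has ended, for whatever reason, the definition cannot be met, however grave a new event is.

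What is at stake is timely safety reporting. Study Aims names safety alongside efficacy, and SAE status is the only trigger that the protocol gives for an immediate IRB report. A grave event in an early participant, arising after drug has ended, has no stated report before the final analysis. Its relation to naloxone need not be judged until data collection is complete, possibly after all 150 planned naloxone patients have been treated.

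**Working it through.** The plan has no figure of its own on this point to reproduce, and the power calculation is not involved. The check is to read the definition, the reporting route and the end of dosing together.

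**Step 1: can the definition be met after drug has ended?** It needs an event that forces naloxone to be stopped. Dosing ends at the earliest of three points: the stopping rule, 48 hours, or discharge. After that point nothing remains to be stopped, so the answer is no.

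**Step 2: is there another route?** I found no second seriousness criterion, no safety window after treatment and no other expedited report in the protocol or its analysis plan.

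**Step 3: apply the text to cases.**

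| Event | Drug status when it arises | SAE as defined? | Stated route |
|---|---|---|---|
| Three of the six listed signs within an hour of a dose | Being given, then stopped | Yes | Immediate IRB report |
| Life-threatening event during the course that forces drug to be stopped | Being given, then stopped | Yes | Immediate IRB report |
| New death or life-threatening event after the course is complete | Ended | No | Final analysis |
| Grave event leading to readmission after a discharge that ended drug | Ended | No | Final analysis, if identified |
| New, separate grave event in a patient stopped earlier for a reaction | Ended | No | Final analysis; the earlier reaction was already reported |

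The dividing line is whether drug has ended. It is not simply the time after the last dose, because an event that stops the drug also follows what becomes the last dose.

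**Step 4: does the uncovered period arise in ordinary patients?** The first dose is at 0900 on the first day after surgery, so a 48-hour course ends at 0900 on the third. The Analysis Plan follows bowel movement to 120 hours from start of surgery. Surgery start times are not given; I assume 0700 to 1700.

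- Start 0700: first dose at 26 h; end of course 26 + 48 = 74 h; remaining 120 − 74 = 46 h.
- Start 1700: first dose at 16 h; end of course 16 + 48 = 64 h; remaining 120 − 64 = 56 h.
- If the schedule means six doses (0, 8, 16, 24, 32 and 40 h), and drug is taken to end with the last of them, the remainders are 120 − 66 = 54 h and 120 − 56 = 64 h.

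On any of these readings, a patient who completes the course is off drug well before the plan's own outcome period closes. Earlier stopping or discharge brings that point forward. These hours show only that the uncovered period is routine; they do not measure risk.

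**The case against.** The strongest case on the other side is that the practical weight is modest. The protocol attributes the expected harms to abrupt opioid reversal and ties its stopping rule to the hour after a dose. A grave event during dosing that leads to stopping is already reported at once. Bedside monitoring is routine care and does not depend on SAE status. Later events remain adverse events and appear in the final analysis. Institutional IRB rules may separately require prompt reports of deaths.

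Most of this stands, and it limits the point. It does not remove the point, because the protocol itself gives staff no instruction to report a new grave event promptly once drug has ended. If the definition was meant to cover events that would have required stopping had drug still been given, it does not say so.

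Four stronger readings might be inferred, and the documents do not support them:

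- *That such events are lost.* They are not; what is missing is SAE status and prompt reporting.
- *That deterioration of the reaction which stopped the drug goes unreported.* The triggering reaction was itself an SAE and was reported at once, so the IRB already knows of the case. The gap concerns a new, separate event.
- *That the share of the 120 hours spent off drug measures the share of serious events missed.* The 120-hour limit is an efficacy censoring time, and the Power Analysis and Analysis Plan differ on its origin. No event rate is given.
- *That counting a mild three-sign reaction as serious is part of the gap.* That is over-reporting, which is conservative and leaves no patient less protected.

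**Conclusion.** The concern holds as a gap in the safety-reporting rule. As written, a new death, life-threatening event or other grave event arising after study drug has ended cannot be an SAE, and the protocol states no immediate report for it. This is a rule that gives the wrong answer, not a detail left out.

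Its size cannot be put as a count or a percentage, because the documents offer no event rate and set no safety follow-up window. The time origin, dose count and surgery start times do not affect the conclusion, which follows from the wording alone. It rests on one reading: that requiring discontinuation presupposes drug still being given. It is a statement about this protocol only; whether institutional rules would fill the gap cannot be seen from it. The change should be made because safety is a stated aim and the remedy is cheap.

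**What to change.** In the Safety Monitoring Plan:

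1. Define seriousness by outcome, whether or not drug is still being given: death; life-threatening event; new or prolonged hospitalisation, including readmission; lasting disability; other important medical event. Readmission needs naming because discharge itself ends study drug.
2. Apply the definition from first dose through a stated window past the end of drug, for example to the later of discharge or the end of the 120-hour outcome period, using one stated time origin. Add any later death or readmission that the study team learns of.
3. State that ileus, constipation or delayed bowel movement that only prolongs stay is recorded as a study outcome and is not expedited unless another criterion is met. Otherwise the prolonged-stay criterion could turn the trial's own outcomes into immediate reports.
4. Give a provisional relatedness judgement with each immediate report. Final adjudication can stay at the end of data collection.
5. Keep study drug discontinuation as its own promptly reported category; Study Design already lists its incidence as an outcome. The stopping rule is unchanged.

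The cost is a wording amendment, some extra IRB reports (the documents do not allow a count) and a chart check for patients discharged before the window closes. A chart check may miss events outside the hospital. If the sponsor wants those captured reliably, patient contact may be needed, at additional cost.

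### Serious adverse events are defined only by the need to stop the drug, so once dosing ends no event, even a death before discharge, qualifies for immediate IRB reporting

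*Combined protocol and SAP*

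**What the plan says.** Section III, Safety Monitoring Plan, defines an adverse event as "Any reported or observed event that is not part of the usual post-operative clinical course". It then adds a single criterion for seriousness: "Serious adverse event: Any event that requires discontinuation of the study drug". The distinction matters because "Any serious adverse events will be reported immediately to the IRB". Other adverse events appear in the final analysis, and study personnel judge their relation to the drug only after data collection is complete.

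The section Toxicities and guidelines for adjustments ranks reversal of central opioid activity, with loss of pain control, as the most uncomfortable or dangerous effect. It continues: "Additional adverse effects include nausea, vomiting, diarrhea, hypertension, tachycardia, diaphoresis, and mental status changes". The stopping rule is: "Study drug will be discontinued in patients who meet any three of six criteria within 1 hour of study drug administration". The six criteria cover heart rate, respiratory rate, sweating, pain score, vomiting and diarrhea. Blood pressure and mental status are not among them.

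Study Assessments and Activities fixes the dosing period: "Oral naloxone 4 mg enterally every 8 hours will be initiated on post-operative day 1 at 0900", and "Study drug will be discontinued as described in the study protocol, after 48 hours, or upon discharge whichever is sooner".

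No section adds a severity criterion such as death, threat to life, a longer stay or lasting harm.

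**The concern.** Immediate reporting exists so that someone outside the study team hears of grave harm while patients are still being enrolled. Here the trigger is tied to an action (stopping the drug) that is possible only while the drug is being given. The same event can be serious one day and not serious the next, with no difference in what happened to the patient.

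Safety is one of the two stated aims (I. Study Aims), and up to 150 patients are to receive naloxone. If a grave event falls outside the definition, the written plan delays its report to the final analysis and its causal assessment to the end of data collection.

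**Working it through.** The plan gives no figure on this point to reproduce, and its power calculation has no bearing on it. The check is to follow the written rules through.

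**1. When an event can qualify.** Inputs: first dose on post-operative day 1 at 0900, dosing every 8 hours, maximum 48 hours (Study Assessments and Activities).
- Latest end of the course: day 1 at 0900 + 48 h = day 3 at 0900.
- Doses fall at 0, 8, 16, 24, 32 and 40 h, which makes 6, or 7 if one is also given at 48 h. With 6 doses, the last drug is given at 40 h, so 48 h is the generous limit.
- If the drug is stopped early, the limit moves forward to that moment. Any later event in that patient cannot require a second stop.
- If the patient is discharged before 48 h, dosing ends at discharge and there is no gap in hospital.

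**2. What happens after that point.** Take a death or a life-threatening event on day 3 at noon in a patient who is still in hospital.
- Does it require discontinuation? No, because there is no drug to discontinue.
- Is it serious as defined? No.
- Must it go to the IRB at once? Not under this plan.
- Is it an adverse event? Yes, so it is reported in the final analysis.

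**3. What happens during dosing.** Take a pain score increase above 50% with hypertension and a mental status change, and no other listed sign.
- Pain: 1 criterion. Hypertension: 0. Mental status change: 0.
- Total 1 + 0 + 0 = 1; the rule needs 3 within 1 hour of a dose.
- The rule does not require a stop, so whether the event is serious depends on a clinician deciding that the drug must stop.

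More generally, there are 2^5 = 32 combinations of the six criteria that include the pain criterion. Six of them (pain alone, 1; pain plus one other, 5) fall short of three, whatever the blood pressure or mental state. This is a count of combinations, not a probability.

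**4. Whether another section closes the gap.** I. Study Design lists the incidence of adverse effects and of drug discontinuation as secondary outcomes. Both are summaries for the analysis, and neither triggers a report.

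**The case against.** The strongest reply is that the definition does not mention the three-of-six rule. It covers any event that requires a stop, and nothing makes that rule the only reason to stop. A clinician who sees severe pain, high blood pressure and confusion can stop the drug, and the event is then serious and reportable. This stands. A reader might infer that the plan leaves such a patient on drug and unreported; the text does not support that, only that the outcome is left to judgement. The example also assumes that no two other listed signs are present, which may not hold in abrupt opioid reversal. The reply does not help after the course ends, because judgement cannot stop a drug that is no longer given.

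Nor are such events lost. All identified adverse events are to be reported in the final analysis and assessed for relation to the drug. Mean pain score and daily opioid requirement on days 0 to 3 are secondary outcomes (I. Study Design) that the Analysis Plan compares with controls, so a reader should not infer that loss of pain control goes unmeasured. The defect concerns when, and on what ground, a grave event is reported.

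A reader might also express the gap as a share of the 120-hour period in the Analysis Plan. That would be wrong: 120 hours is the censoring limit for time to first bowel movement, and no section sets it as a safety follow-up period.

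**Conclusion.** The point holds as a defect in the definition. As written, seriousness follows dosing status. From post-operative day 3 at 0900 at the latest, and sooner after an early stop, no event before discharge can be serious. This follows from the text and needs no assumption beyond the patient still being in hospital. During dosing the gap is narrower: for a pain increase with hypertension and mental status change, the stop and the immediate report are discretionary.

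The size in events is unknown, because the documents give neither an incidence of grave events nor an expected length of stay. The primary analysis and the planned pain and opioid comparisons are unaffected. A reader might go further and conclude that the six-criterion stopping rule is itself wrong because it omits two named effects. The documents do not settle that: adding criteria would stop treatment in more patients, which is a clinical trade-off for the investigators. The change should be made because it concerns participant protection and costs little.

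**What to change.** In section III, Safety Monitoring Plan, replace the definition with one based on severity and outcome. Suggested content: an event from first dose to discharge that is fatal, is life-threatening, prolongs the stay, causes lasting harm, or needs urgent treatment to prevent one of these, whether or not the drug is stopped.

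Keep any event that requires stopping the drug as an additional trigger for immediate IRB reporting, so that nothing now reportable is lost. Ileus that does no more than prolong the stay could be exempted, since ileus and length of stay are already secondary outcomes. Final wording is for the investigators and the IRB.

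The amendment closes the gap after dosing. During dosing it makes the example in step 3 reportable if it reaches one of the severity criteria; a mild, transient episode would still rest on judgement. The stopping rule, the outcomes and the sample size stay as they are. The cost is a short protocol amendment and a few more IRB reports.
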